#### 11.3.2 Bilirubin

Total bilirubin > ULN but ≤ 1.5 X ULN: May hold treatment, treat at full dose, or treat at reduced dose, at the discretion of the investigator

Total bilirubin > 1.5 X ULN: Hold treatment until serum total bilirubin is ≤ 1.5 X ULN (maximum 21 days), then re-treat at next lower dose level

## 11.4 Renal Toxicity

If serum creatinine is  $\geq 1.5$  on planned treatment date, estimate the creatinine clearance (CrCl) by the Cockcroft and Gault Equation.

Calculated Creatinine Clearance (CrCl)	Management
$\geq 45$ ml/min	Hydrate as clinically indicated. May treat at full dose, treat at next lower dose level of ribavirin, or hold treatment, at the discretion of the investigator.
$< 45$ ml/min	Hold treatment for the week and hydrate as clinically indicated.  If repeat CrCl $\geq 45$ ml/min, may resume treatment at the next lower dose level of ribavirin

## 11.5 Diarrhea

### Grade 1 or Grade 2 Diarrhea:

Ribavirin treatment may be continued at full dose, continued at the next lower dose level, or held. Antidiarrheals may be used as needed. Dose reduction is at the discretion of the investigator.

### Grade 3 Diarrhea:

In the event of diarrhea requiring hospitalization (ie, Grade 3), supportive measures may include hydration, octreotide, and antidiarrheals.

Ribavirin treatment will be held until diarrhea has improved to  $\leq$  Grade 1, with dose reductions as follows:

If Grade 3 diarrhea duration is  $\leq 48$  hours, the next treatment may be given at full dose or at the next lower dose level, at the discretion of the investigator.

If Grade 3 diarrhea duration is  $> 48$  hours, subsequent ribavirin should be given at the next lower dose level

### Grade 4 Diarrhea:

Off Study (if felt to be treatment related)

## 11.6 Nausea/Vomiting

## MEMORIAL SLOAN-KETTERING CANCER CENTER

IRB#: 14-211 A (7)

APPROVED: 19 DEC 2016

Prophylactic anti-emetics are not planned. However, for any patient experiencing nausea, use of anti-emetics is at the discretion of the investigator.

For any patient experiencing  $\geq$  Grade 3 nausea  $> 72$ h and/or  $\geq$  Grade 3 vomiting  $> 24$ h during a cycle, if felt to be possibly related to ribavirin, then upon resolution of these toxicity(ies) to  $\leq$  Grade 1, ribavirin may be resumed at the next lower dose level of ribavirin. Anti-emetics may be incorporated at the discretion of the investigator.

### 11.7 Non-hematologic toxicity not otherwise specified

Dose delay and/or dose reduction is optional at the discretion of the investigator as regards the following  $\geq$  grade 3 adverse events: dental adverse events, hearing-related adverse events, INR or aPTT elevation, insomnia, weight gain or weight loss, SIADH, low bicarbonate, low albumin, hypophosphatemia. Similarly, the decision regarding whether to institute dose modifications for grade 2 or 3 fatigue will be at the discretion of the investigator.

For non-hematologic toxicity not otherwise specified:

$\geq$  Grade 3: Interrupt until resolved to  $\leq$  grade 1, then:  
If resolution to grade  $\leq 1$  in  $\leq 7$  days, resume ribavirin at the current dose level or at next lower dose level, at investigator discretion  
If resolution to grade  $\leq 1$  in  $> 7$  days, resume ribavirin at one lower dose level

## 12.0 CRITERIA FOR THERAPEUTIC RESPONSE/OUTCOME ASSESSMENT

Response and progression will be evaluated in this study using modified international criteria proposed by the revised Response Evaluation Criteria in Solid Tumors (RECIST) guideline (version 1.1) [38]. Changes in the largest diameter (unidimensional measurement) of the tumor lesions and the shortest diameter in the case of malignant lymph nodes are used in the RECIST criteria. The schedule for scan assessments is provided in Section 10.

### 12.1.1 Definitions

Evaluable for toxicity. All patients will be evaluable for toxicity from the time of their first treatment on study.

Evaluable for objective response. Only those patients who have measurable disease present at baseline, have received at least one cycle of therapy, and have had their disease re-evaluated will be considered evaluable for response. These patients will have their response classified according to the definitions stated below. (Note: Patients who exhibit objective disease progression prior to the end of cycle 1 will also be considered evaluable.)

Evaluable Non-Target Disease Response. Patients who have lesions present at baseline that are evaluable but do not meet the definitions of measurable disease, have received at least one cycle of therapy, and have had their disease re-evaluated will be considered evaluable for non-target disease. The response assessment is based on the presence, absence, or unequivocal progression of the lesions.

### 12.1.2 Disease Parameters

**Measurable disease.** Measurable lesions are defined as those that can be accurately measured in at least one dimension (longest diameter to be recorded) as  $\geq 20$  mm by chest x-ray, as  $\geq 10$  mm with CT scan, or  $\geq 10$  mm with calipers by clinical exam. All tumor measurements must be recorded in millimeters (or decimal fractions of centimeters).

Note: Tumor lesions that are situated in a previously irradiated area might or might not be considered measurable. If the investigator thinks it appropriate to include them, the conditions under which such lesions should be considered must be discussed with the principle investigator.

**Malignant lymph nodes.** To be considered pathologically enlarged and measurable, a lymph node must be  $\geq 15$  mm in short axis when assessed by CT scan (CT scan slice thickness recommended to be no greater than 5 mm). At baseline and in follow-up, only the short axis will be measured and followed.

**Non-measurable disease.** All other lesions (or sites of disease), including small lesions (longest diameter  $<10$  mm or pathological lymph nodes with  $\geq 10$  to  $<15$  mm short axis), are considered non-measurable disease. Bone lesions, leptomeningeal disease, ascites, pleural/pericardial effusions, lymphangitis cutis/pulmonitis, inflammatory breast disease, and abdominal masses (not followed by CT or MRI), are considered as non-measurable.

Note: Cystic lesions that meet the criteria for radiographically defined simple cysts should not be considered as malignant lesions (neither measurable nor non-measurable) since they are, by definition, simple cysts.

'Cystic lesions' thought to represent cystic metastases can be considered as measurable lesions, if they meet the definition of measurability described above. However, if non-cystic lesions are present in the same patient, these are preferred for selection as target lesions.

**Target lesions.** All measurable lesions up to a maximum of 2 lesions per organ and 5 lesions in total, representative of all involved organs, should be identified as **target lesions** and recorded and measured at baseline. Target lesions should be selected on the basis of their size (lesions with the longest diameter), be representative of all involved organs, but in addition should be those that lend themselves to reproducible repeated measurements. It may be the case that, on occasion, the largest lesion does not lend itself to reproducible measurement in which circumstance the next largest lesion which can be measured reproducibly should be selected. A sum of the diameters (longest for non-nodal lesions, short axis for nodal lesions) for all target lesions will be calculated and reported as the baseline sum diameters. If lymph nodes are to be included in the sum, then only the short axis is added into the sum. The baseline sum diameters will be used as reference to further characterize any objective tumor regression in the measurable dimension of the disease.

**Non-target lesions.** All other lesions (or sites of disease) including any measurable lesions over and above the 5 target lesions should be identified as **non-target lesions** and should also be recorded at baseline. Measurements of these lesions are not required, but the presence, absence, or in rare cases unequivocal progression of each should be noted throughout follow-up.

### 12.1.3 Methods for Evaluation of Measurable Disease

## MEMORIAL SLOAN-KETTERING CANCER CENTER

IRB#: 14-211 A (7)

APPROVED: 19 DEC 2016

All measurements should be taken and recorded in metric notation using a ruler or calipers. All baseline evaluations should be performed as closely as possible to the beginning of treatment and never more than 4 weeks prior to registration.

The same method of assessment and the same technique should be used to characterize each identified and reported lesion at baseline and during follow-up. Imaging-based evaluation is preferred to evaluation by clinical examination unless the lesion(s) being followed cannot be imaged but are assessable by clinical exam.

Clinical lesions Clinical lesions will only be considered measurable when they are superficial (e.g., skin nodules and palpable lymph nodes) and  $\geq 10$  mm diameter as assessed using calipers (e.g., skin nodules). In the case of skin lesions, documentation by color photography, including a ruler to estimate the size of the lesion, is recommended.

Chest x-ray Lesions on chest x-ray are acceptable as measurable lesions when they are clearly defined and surrounded by aerated lung. However, CT is preferable.

Conventional CT and MRI This guideline has defined measurability of lesions on CT scan based on the assumption that CT slice thickness is 5 mm or less. If CT scans have slice thickness greater than 5 mm, the minimum size for a measurable lesion should be twice the slice thickness. MRI is also acceptable in certain situations (e.g. for body scans).

### 12.1.4 Response Criteria

#### 12.1.4.1 Evaluation of Target Lesions

Complete Response (CR): Disappearance of all target lesions. Any pathological lymph nodes (whether target or non-target) must have reduction in short axis to  $<10$  mm.

Partial Response (PR): At least a 30% decrease in the sum of the diameters of target lesions, taking as reference the baseline sum diameters.

Progressive Disease (PD): At least a 20% increase in the sum of the diameters of target lesions, taking as reference the smallest sum on study (this includes the baseline sum if that is the smallest on study). In addition to the relative increase of 20%, the sum must also demonstrate an absolute increase of at least 5 mm. (Note: the appearance of one or more new lesions is also considered progressions).

Stable Disease (SD): Neither sufficient shrinkage to qualify for PR nor sufficient increase to qualify for PD, taking as reference the smallest sum diameters while on study.

#### 12.1.4.2 Evaluation of Non-Target Lesions

Complete Response (CR): Disappearance of all non-target lesions and normalization of tumor marker level. All lymph nodes must be non-pathological in size ( $<10$  mm short axis).

Note: If tumor markers are initially above the upper normal limit, they must normalize for a patient to be considered in complete clinical response.

Non-CR/Non-PD: Persistence of one or more non-target lesion(s) and/or maintenance of tumor marker level above the normal limits.

## MEMORIAL SLOAN-KETTERING CANCER CENTER

IRB#: 14-211 A (7)

APPROVED: 19 DEC 2016

**Progressive Disease (PD):** Appearance of one or more new lesions and/or *unequivocal progression* of existing non-target lesions. *Unequivocal progression* should not normally trump target lesion status. It must be representative of overall disease status change, not a single lesion increase.

Although a clear progression of “non-target” lesions only is exceptional, the opinion of the treating physician should prevail in such circumstances, and the progression status should be confirmed at a later time by the review panel (or Principal Investigator).

### 12.1.4.3 Evaluation of Best Overall Response

The best overall response is the best response recorded from the start of the treatment until disease progression/recurrence (taking as reference for progressive disease the smallest measurements recorded since the treatment started). The patient's best response assignment will depend on the achievement of both measurement and confirmation criteria.

## For Patients with Measurable Disease (i.e., Target Disease)

Target Lesions	Non-Target Lesions	New Lesions	Overall Response	Best Overall Response when Confirmation is Required*
CR	CR	No	CR	$\geq 4$ wks. Confirmation**
CR	Non-CR/Non-PD	No	PR	$\geq 4$ wks. Confirmation**
CR	Not evaluated	No	PR	
PR	Non-CR/Non-PD/not evaluated	No	PR	
SD	Non-CR/Non-PD/not evaluated	No	SD	documented at least once $\geq 4$ wks. from baseline**
PD	Any	Yes or No	PD	no prior SD, PR or CR
Any	PD***	Yes or No	PD	
Any	Any	Yes	PD	

\* See RECIST 1.1 manuscript for further details on what is evidence of a new lesion.  
 \*\* Only for non-randomized trials with response as primary endpoint.  
 \*\*\* In exceptional circumstances, unequivocal progression in non-target lesions may be accepted as disease progression.

**Note:** Patients with a global deterioration of health status requiring discontinuation of treatment without objective evidence of disease progression at that time should be reported as "*symptomatic deterioration*." Every effort should be made to document the objective progression even after discontinuation of treatment.

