#### 12.1.6 Progression-Free Survival

PFS is defined as the duration of time from start of treatment to time of progression or death, whichever occurs first.

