## MEMORIAL SLOAN-KETTERING CANCER CENTER

IRB#: 14-211 A (7)

APPROVED: 19 DEC 2016

Participants can be removed from the study at any time if the study doctor feels that it is in their best interest to do so.

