### 14.0 BIOSTATISTICS

A sample size of 12 patients will be accrued and followed until progression of disease (or until removal of study for other medical/logistical reasons), in this pilot study with the objective to obtain preliminary evidence of efficacy in the selected patient population of R/M HPV related malignancies. Radiographic responses, determined by RECIST 1.1 criteria, will be tabulated by adding partial responses and complete responses (CR + PR). The best response for each patient during the study will be used.

Efficacy considerations for the statistical design of this study are informed by historical data regarding second-line or greater systemic therapy for patients with recurrent/metastatic (R/M) head and neck cancer, cervical cancer, or anal cancer. Among patients with R/M head and neck cancer, the historical estimate for objective response rate with palliative chemotherapy after first line is 15% [39, 40]. Similarly, the response rate of palliative single agent chemotherapy for advanced cervical cancer is approximately 15-20% [41, 42]. For R/M anal cancer, no regimen has been shown to be effective after first line platinum + 5-fluorouracil [43].

The regimen would be considered worthy of further study if radiographic responses are observed in at least 2 of 12 subjects. The probability of missing an effect (observing 0 or 1 responses out of 12 patients if the true response rate is 30%), is 0.09. Overall Survival and Progression-Free Survival will be estimated with the Kaplan-Meier method.

Tissue correlative studies will be for purposes of hypothesis generation. We will explore if the anti-Gli-1 IHC score (scale 0-3 dichotomized to low/high) is related to response (CR+PR) using Chi-square or Fisher's exact test. The following provisional scoring system will be used (% refers to percentage of tumor cells that stain positively [cytoplasm and/or nucleus] for Gli 1):

IHC score 0: <=5%

IHC score 1: >5 and <=30%

IHC score 2: >30% and <=50%

IHC score 3: >50%

Additionally, baseline and post-progression Gli-1 expression will be reported (using this provisional scoring system) among the patients who have an initial radiographic response and a post-progression biopsy.

The number and grade of toxicities will be tabulated using NCI CTCAE version 4, as well as the number of dose reductions in all cycles.

The projected accrual rate is 1 to 2 patients per month.

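### A patient who stops for symptomatic deterioration and then leaves follow-up would be censored in the Kaplan-Meier PFS for a reason tied to prognosis, because the follow-up passages are not reconciled

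*Combined protocol and SAP*

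**What the plan says.** - **PFS event.** Section 12.1.6 measures PFS "from start of treatment to time of progression or death, whichever occurs first". Section 12.0 states which criteria apply: "Response and progression will be evaluated in this study using modified international criteria proposed by the revised Response Evaluation Criteria in Solid Tumors (RECIST) guideline". Sections 12.1.4.1 and 12.1.4.2 then define progressive disease by growth of target lesions, new lesions or unequivocal worsening of non-target disease. No other definition of progression is given.
- **Symptomatic deterioration.** The note under the best-response table for measurable disease gives a separate label to "Patients with a global deterioration of health status requiring discontinuation of treatment without objective evidence of disease progression at that time". It continues: "Every effort should be made to document the objective progression even after discontinuation of treatment".
- **End of follow-up.** Section 14.0: "A sample size of 12 patients will be accrued and followed until progression of disease (or until removal of study for other medical/logistical reasons". Section 13.0 adds: "Participants can be removed from the study at any time if the study doctor feels that it is in their best interest to do so".
- **Contact and imaging after stopping.** Sections 1.0 and 4.3 include a scan at the end of treatment. Section 9.1 and the Section 10.0 table do not repeat it, and the table's post-treatment column marks no imaging. The one scheduled later contact is a visit about 30 days after the last dose, for patients still in active follow-up. Section 9.1 says that missing it for medical or logistical reasons is not a violation.
- **Analysis.** Section 14.0 names Kaplan-Meier for overall survival and PFS and gives no censoring rule. Section 2.0 lists both as secondary objectives, to be described.

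**The concern.** Kaplan-Meier assumes that a patient censored today has the same outlook as those still being followed. A patient who stops because of global decline plainly may not. If such a patient has no RECIST progression on record and follow-up ends at removal, the likely early failures drop out of the risk set without being counted, and the curve sits too high.

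The situation is realistic under the scan schedule. The first on-treatment scan falls in the last week of cycle 2, around week 8 (2 × 28 = 56 days). After cycle 4 the gap may widen to three cycles (3 × 28 = 84 days, or 12 weeks). A patient can decline between scans. With 12 patients, each one is 1/12, or 8.3%, of the sample, so one or two unspecified cases visibly move the curve.

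**Working it through.** **The plan's own figure.** Section 14.0 gives one calculated design figure: a probability of 0.09 of seeing 0 or 1 responses in 12 patients at a true rate of 30%. Check: 0.7^12 + 12 × 0.3 × 0.7^11 = 0.0138 + 0.0712 = 0.0850, which rounds to 0.09. It reproduces, but it concerns response only. The plan states no PFS figure.

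**One patient traced through the text.**
1. The patient stops for global decline. Section 12 labels this symptomatic deterioration, which is not progressive disease.
2. If the end-of-treatment scan in Sections 1.0 and 4.3 is done and shows RECIST progression, the patient has a PFS event and the problem does not arise.
3. If the scan shows no progression, or is not done, there is no event yet. Section 12 asks for later documentation, while Section 14.0 allows follow-up to end at removal.
4. If follow-up does end, there is no event and no further observation, so Kaplan-Meier can only censor at last contact.

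**Inputs for the size.** From the documents: n = 12. Assumed, because the documents give nothing: k = 1 to 4 patients stop this way; failure times are exponential with a 2-month median when deterioration counts as failure, so that 2-month PFS is 50%; and deterioration is equally likely to be the form of failure at any time.

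**No later capture.** A share k/12 of failures is censored at the moment of failure, so the estimated hazard is multiplied by (1 − k/12). The 2-month estimate is 0.5^(1 − k/12) and the apparent median is 2/(1 − k/12) months.

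**Capture one month later.** The k patients have their event one month after stopping. The 2-month figure is (1 − k/12) × 0.5 + (k/12) × 0.5^(1/2) = 0.5 + (k/12) × (0.7071 − 0.5).

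| k of 12 | 2-month PFS, no capture | Apparent median (months) | 2-month PFS, capture after 1 month |
|---|---|---|---|
| 0 | 50.0% | 2.00 | 50.0% |
| 1 | 53.0% (simulated 52.7%) | 2.18 | 51.7% (simulated 51.4%) |
| 2 | 56.1% (55.8%) | 2.40 | 53.5% (53.2%) |
| 3 | 59.5% (59.0%) | 2.67 | 55.2% (55.3%) |
| 4 | 63.0% (62.5%) | 3.00 | 56.9% (56.7%) |

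The simulated values are means over 4,000 simulated Kaplan-Meier curves of 12 patients.

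**Reading the two PFS columns.** Both exceed the curve that counts deterioration as failure. Against the protocol's own definition, however, the last column is correct: the event is dated when progression or death occurs. If a one-month delay were the truth, the error due to censoring alone would be the gap between the columns, from 53.0 − 51.7 = 1.3 points (k = 1) to 63.0 − 56.9 = 6.1 points (k = 4).

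**Sensitivity to the delay.** With a fixed two-month delay no such patient can have an event by month 2, so the figure is 0.5 + (k/12) × 0.5, or 54.2% to 66.7%. This lies above the no-capture column at that time point. An upward bias against the protocol definition therefore requires removed patients to progress or die sooner than those who stay. Global deterioration makes that likely, but the documents do not quantify it.

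**Sampling error.** At 50% with 12 patients, the 95% half-width is about 1.96 × √(0.25/12) = 0.28, or 28 points.

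**The case against.** The strongest reply is that the plan is under-specified rather than wrong. It calls for an end-of-treatment scan, asks explicitly for progression to be documented after stopping, and counts death as an event. The overall-survival objective implies some follow-up for death, and Section 17.3 makes deaths reportable for 30 days after the last treatment. No censoring rule is written. Section 12.1.6 does not use the word objective, although Section 12.1.5 requires objective documentation of progression when measuring duration of response. Any shift is also small beside a 28-point half-width.

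Much of this stands, and it rules out three stronger readings:
- A reader might infer that every patient who deteriorates will be censored and that PFS is certainly biased. The documents do not support that. Where the scan shows progression, or later progression or death is captured, the patient counts as an event.
- A reader might infer from the Section 10.0 table that later progression cannot be documented. Sections 1.0 and 4.3 contradict the table on the end-of-treatment scan, so the table alone does not settle it.
- A reader might infer that an inflated PFS would be set against historical PFS and favour the drug. The only historical figures in Section 14.0 are response rates, and the decision rests on at least 2 responses in 12.

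The reply does not remove the gap. The scan settles only those patients whose progression it shows, and Section 9.1 and the table leave it out. Survival follow-up has no schedule. After 30 days, only events at least possibly related to treatment must be reported. No definition of progression other than RECIST exists. Section 14.0 states in plain words that follow-up may end at removal. Sampling error does not excuse a systematic shift, because the confidence interval does not allow for it.

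**Conclusion.** The point holds as a conditional one. A patient who stops for deterioration, has no RECIST progression at the end-of-treatment scan (or no scan) and leaves follow-up as Section 14.0 permits would be censored for a reason related to prognosis. That biases the Kaplan-Meier PFS upward.

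The size depends on how many such patients occur and whether their later progression or death is captured, and neither can be derived from the documents. Relative to counting deterioration as failure, with 1 to 4 of 12 patients and 2-month PFS of 50%, the estimate is about 53% to 63% without capture and about 51% to 57% with capture after one month. The 2-month median, the exponential form, k and the one-month delay are all assumptions.

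The consequence is limited to a descriptive secondary endpoint in a 12-patient pilot. The response-based decision rule and its 0.09 are untouched. The change is worth making because it is cheap and removes a conflict within the plan.

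**What to change.** 1. In Sections 13.0 and 14.0, state that patients who stop treatment without objective progression stay in follow-up for progression and death. This brings Section 14.0 into line with the Section 12 note on symptomatic deterioration.
2. Reconcile the end-of-treatment scan in Sections 1.0 and 4.3 with Section 9.1 and the Section 10.0 table.
3. In Section 14.0, state the PFS censoring rule. Beside PFS as defined in Section 12.1.6, add one sensitivity Kaplan-Meier estimate that counts symptomatic deterioration as an event on the date of discontinuation.

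The cost is a little more chart follow-up, part of which overall survival already needs, and one extra curve. The sensitivity figure will be less favourable and includes an event that rests on the investigator's judgement. For that reason it should accompany the protocol definition and not replace it.
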